## Synopsis

**Study title:** Targeted Interventions to Prevent Chronic Low Back Pain in High Risk Patients: A Multi-Site Pragmatic RCT (TARGET Trial)

### Objectives:

Low back pain (LBP) is one of the most prevalent and potentially disabling conditions for which people seek health care. Patients, providers, and payers are in agreement that greater effort needs to be directed toward prevention of the transition from acute to chronic LBP. Chronic LBP is painful, disabling and expensive (from a patient's perspective), extremely difficult to manage (from a provider's perspective), fraught with inefficiencies including unnecessary exposure to expensive tests and risky procedures (from a payer's perspective), and may contribute to opioid dependence and abuse (from society's perspective). With the majority of patients who experience acute LBP seeking care from their primary care physician (PCP), this study will compare common, pragmatic, evidence-based, and patient-centered approaches emanating from the PCP environment to reduce the proportion of people with acute LBP who transition to chronic LBP and improve functional abilities.

The research question to be addressed with the present study is:

**For patients with acute LBP deemed high risk to transition to chronic LBP, does prompt referral to psychologically informed physical therapy (PIPT) reduce the rate of transition to chronic LBP and improve functional abilities?**

To answer this question, we will compare:

1. A Guideline-Based Care (GBC) arm (comparator arm) in which management decisions are made between PCPs and patients with the guidance of best evidence but with no specific directives; and
2. A Guideline-Based Care plus Psychologically Informed Physical Therapy (GBC+PIPT) arm (intervention arm) in which PCP care is enhanced with a prompt referral to physical therapy (PT) that includes psychologically informed coaching directed towards education and reduced fear of movement.

### Specific aims:

Primary Aims: For patients with acute LBP deemed high risk to transition to chronic LBP, determine the effect of prompt referral to PIPT in (1) preventing transition to chronic LBP and (2) improving functional abilities.

Secondary Aims: (1) Measure use of medical resources for treatment of LBP for those patients categorized as high risk at presentation; and (2) Describe rates of transition from acute to chronic LBP, functional ability, and use of medical resources for patients categorized as low or medium risk at presentation to their PCP.

Hypotheses: The combined GBC+PIPT intervention arm for high risk patients will be more effective than the GBC comparator arm alone in (1) preventing patients with acute LBP from developing chronic LBP, (2) improving functional outcomes, and (3) reducing medical resource utilization for the treatment of LBP.

**Design and outcomes:**

The primary randomized controlled trial (RCT) cohort study is a multi-site cluster RCT comparing GBC versus GBC+PIPT for patients with acute LBP at high risk for transition to chronic LBP, as determined by the STarT Back Screening Tool. A secondary, prospective, observational cohort study will be conducted for those patients presenting with acute LBP who are at low or medium risk for chronic LBP as measured with the STarT Back Tool.

The STarT Back Tool is a 9-item, validated questionnaire for use in the PCP setting to screen patients with acute LBP for prognostic indicators of transition to chronic LBP. The tool groups patients into low, medium, and high risk categories. Though the tool was developed and tested with European samples, there is emerging evidence to support its use in the US. Recruitment will include a minimum of 12 PCP clinics within each of five geographical areas (Pittsburgh, PA; Boston, MA; Baltimore, MD; Charleston, SC; Salt Lake City, UT). Each PCP clinic will be cluster randomized to one of two arms of the trial.

The primary outcome measures of the study are the presence or absence of chronic LBP and functional ability, determined by the Oswestry Low Back Pain Disability Index (Oswestry), at 6 months in the high risk group. A secondary outcome measure is medical resource utilization related to LBP (e.g., imaging, epidural steroid injections, prescribed medications, surgery) determined through electronic medical record (EMR) data.

**Interventions and duration:**

This research study is built upon a quality improvement (QI) initiative that includes 1) collection of patient-reported outcomes in all primary care settings and 2) prompt referral to PIPT for patients with high risk acute LBP in the intervention settings. All PCPs part of the initiative will receive a primer on current evidence-based clinical care guidelines for the treatment of acute LBP. All PCP practices will receive QI instruction on how to collect data for the Chronic LBP Questionnaire, the Oswestry LBP Questionnaire, and the STarT Back Tool, which will be given to clinicians and PCPs through the EMR. Clinicians in the intervention settings will also receive QI instruction and EMR tools to refer patients with high risk acute LBP to a PT practice where physical therapists have been trained in PIPT methods. Patients in the GBC comparator arm will receive care from their PCP based on best evidence but with no specific directives or prompts for referrals. Recruiting for participation in the research study will occur at each of the five sites for 15-26 months.

**Sample size and population:**

Plans are to enroll 1,860 high risk patients for the RCT. The observational cohort will consist of 6,900 low and medium risk patients. Both groups will be followed for 12 months.

# 1 Study objectives

The target population for this study is adult patients who present to PCPs (i.e., internal medicine, family practice, and geriatric medicine physicians) to receive care for back pain during the primary care clinic visit. To distinguish “acute” versus “chronic” LBP, a 2-question screen based on criteria developed by the NIH Research Task Force on Chronic Low Back Pain will be used: 1) How long has low back pain interfered with your ability to do regular daily activities? 2) Think only about the past 6 months. How often has low back pain interfered with your ability to do regular daily activities? A response of “more than three months” to question 1, and a response of “half the days or more than half the days” to question 2 will define chronic LBP. By definition, all other patients will be defined as having acute LBP. Patients will be excluded who have medical contraindications to PT (“red flags”) based on the judgement of the PCP as documented in the EMR.

## 1.1 Primary objective

The primary aims (PA1 and PA2) of this pragmatic clustered RCT and the primary hypotheses (H1 and H2) are:

- 1.1.1 **PA1:** In patients with acute LBP who are deemed “high risk” for transition to chronic (RCT cohort), two study arm treatments will be compared, 1) GBC and 2) GBC+PIPT, and the proportion of this cohort that transition to chronic LBP at the 6-month assessment.
- 1.1.2 **H1:** GBC+PIPT will be more effective than GBC alone for preventing patients with high risk acute LBP from developing chronic LBP.
- 1.1.3 **PA2:** Compare between the two study arms LBP-related function (e.g., lifting, walking, sleeping) for high risk patients using the Oswestry at 6 months.
- 1.1.4 **H2:** GBC+PIPT will be more effective than GBC alone for improving functional outcomes for patients with high risk acute LBP.

## 1.2 Secondary objectives

Secondary aims (SA) and relevant hypotheses are:

- 1.2.1 **SA3:** Compare between the two study arms acute LBP-related medical resource utilization (e.g., imaging, epidural steroid injections, opioids) for high risk patients.
- 1.2.2 **H3:** GBC+PIPT will be more effective than GBC alone for reducing LBP-related medical resource utilization for patients with high risk acute LBP.
- 1.2.3 **SA4:** Follow patients with acute LBP who are deemed “low and medium risk” in an observational cohort to determine the proportion that transitions to chronic LBP at 6 months, assess functional outcomes at 6 months, and measure LBP-related medical resource utilization at 12 months.

- 1.2.4 **SA5:** Conduct subgroup analyses for PA1-2 and SA3-4 on patients with lower socioeconomic status (using Medicaid or no insurance as a proxy) and the co-morbid conditions of smoking, depression, and obesity.
- 1.2.5 **H5:** GBC+PIPT will have lower transition to chronic LBP and will be more effective than GBC alone for improving functional outcomes and reducing LBP-related medical resource utilization for the subgroup of patients with depression or low socioeconomic status. Because the interventions being studied do not specifically target obesity and smoking, and the influence of smoking and obesity on the progression of acute to chronic LBP is uncertain, group x obesity or smoking interactions are not expected.

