### 3.4 Study population and sites

The target population for this study will be adult patients who present to primary care physicians (i.e., internal medicine, family practice, and geriatric medicine physicians) with a primary complaint of LBP. Patients will be recruited from health systems in five regional areas that surround: 1) Pittsburgh, PA (UPMC); 2) Boston, MA (Boston Medical Center); 3) Baltimore, MD (Johns Hopkins Medicine); 4) Charleston, SC (Medical University of South Carolina); and 5) Salt Lake City, UT (Intermountain Healthcare). Within the individual regional areas, primary care clinics have been identified that represent community-based PCP clinics. In all instances, there are more potential sites than are required for successful completion of the trial, which will allow flexibility in the randomization scheme and alternatives should there be individual PCP-clinic recruitment shortfalls. This large, nation-wide group of clinics across five different health systems provides a high level of pragmatism for the PRECIS-2 organizational domain because the systems will be variable with regards to provider expertise, resources, and organizational structure.

Certain patient subgroups are of particular interest (**SA5**) given greater risk for poorer LBP outcomes as demonstrated in observational cohort studies. Adequate enrollment will be assured to have statistical power to conduct subgroup analyses of patients with lower socioeconomic status (using insurance as a proxy) and the comorbid conditions of smoking, depression, and obesity. Identification of subgroups will be based on information obtainable in the EMR. The participating primary care clinics will be sampled to reflect gender, race, and ethnicity proportions of the population being served at the recruitment sites.

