## 9 Statistical considerations

### 9.1 General design issues

- 9.1.1 **A primary aim (PA1)** is to determine in patients with acute LBP who are deemed high risk for transition to chronic, what is the proportion of patients transitioning to chronic LBP by the time of the 6-month assessment who are treated with 1) GBC compared to 2) GBC+PIPT.
- 9.1.2 **H1:** GBC+PIPT will be more effective than GBC alone for preventing patients with high risk acute LBP from transitioning to chronic LBP.
- 9.1.3 The primary outcome will be determined by patients' responses to the Chronic LBP Questionnaire at 6 months. The proportion of patients that have transitioned will be compared across the two study arms.
- 9.1.4 **PA2** is to compare patient-centered outcomes of LBP-related function (e.g., lifting, walking, sleeping) for high risk patients between the two study arms at the 6-month assessment.
- 9.1.5 **H2:** GBC+PIPT will be more effective than GBC alone for improving functional outcomes for patients with high risk acute LBP.
- 9.1.6 This primary outcome will be measured using patients' responses to the Oswestry LBP Questionnaire at baseline versus at 6 months to determine changes in the score.
- 9.1.7 **SA3** is to compare acute LBP-related medical resource utilization (e.g., imaging, epidural steroid injections, opioids) for high risk patients between the two study arms.

- 9.1.8 **H3:** GBC+PIPT will be more effective than GBC alone for reducing LBP-related medical resource utilization for patients with high risk acute LBP.
- 9.1.9 This secondary outcome will be measured by retrieving patient medical resource utilization data from the EMR for LBP-related tests, procedures, specialty visits, and pharmaceuticals for 12 months after the initial visit.
- 9.1.10 **SA4** is related to PA1-2 and SA3 but will determine the proportion of medium and low risk patients that transitions to chronic LBP; patient-centered outcomes (e.g., functional impact); and LBP-related medical resource utilization.
- 9.1.11 Outcomes for this aim will utilize the same measures and sources as PA1-2 and SA3 for the medium and low risk patients.
- 9.1.12 **SA5** is to conduct subgroup analyses for PA1-2 and SA3 on patients with lower socioeconomic status (using insurance as a proxy) and the co-morbid conditions of smoking, depression, and obesity.

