- 9.1.13 **H5:** GBC+PIPT will have less transition to chronic LBP and will be more effective than GBC alone for improving functional outcomes and reducing LBP-related medical resource utilization for the subgroup of patients who are underserved or with depression. Because the interventions being studied do not specifically target obesity and smoking, and the relationship of these variables to transition to chronic are unclear, group x obesity interactions are not expected.
- 9.1.14 Outcomes for this aim will utilize the same measures and sources as PA1-2, SA3 but will also include EMR data on patient co-morbidities, smoking status, and socioeconomic status.
- 9.1.15 **Missing data:** Baseline characteristics, such as age, gender, and health insurance status, will be compared between patients with complete assessment data to those with missing data by treatment group in order to assess potential biases that may exist in the complete case analysis. Sensitivity analyses for the primary and secondary outcomes will be conducted using several methods, which have different missing data assumptions.
- 1) Complete case analyses, which assumes missing data are completely at random,
  - 2) Multiple imputation using M=10 imputations, which assumes missing at random, and
  - 3) Assigning poor scores and good scores for missing values differentially by treatment group, which aligns with non-ignorable missingness (the data missingness is nonrandom and related to the actual value).

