- 9.2.4 **Treatment assignment procedures:** Detecting an interaction effect the same size as the overall intervention effect would require a four-fold increase in the effective sample size (more clinics and patients accounting for clustering), which is not feasible. There will be sufficient power to detect stronger intervention effects in some *a priori* defined subgroups at the participant level (smoking, depression, obesity, lower SES) if the cohort is evenly split.
- 9.2.5 **Analysis of randomization:** Distributions of baseline characteristics for clinics and patients will be compared between the study arms to assess effectiveness of the randomization, and statistical or clinical differences will be adjusted for in sensitivity analyses. All analyses for treatment group comparisons will use an intention-to-treat approach and results will be reported using the CONSORT extension to cluster randomized trials. This approach is highly pragmatic per the PRECIS-2 primary analysis domain.

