## 9.5 Data analyses

- 9.5.1 **Primary outcome 1:** This initial analysis (**PA1**) will use a generalized linear mixed model with a logit link controlling for block set (see Randomization) and a fixed effect for intervention accounting for the cluster RCT design with a random clinic effect. Primary analyses will also adjust for patient characteristics (maladaptive pain coping behaviors such as catastrophizing and fear avoidance, functional impairment as measured by the Oswestry, and presence

of psychiatric comorbidities), as these have been associated with higher transition to chronic LBP. The intraclass correlation coefficients will also be estimated and reported for all outcome measures to assess the assumptions for sample size analyses and also for future investigations using similar designs and outcomes. Analysis for the secondary aims (**SA4** and **SA5**) will be largely descriptive assessing the proportion of patients who transition to chronic LBP among the low and moderate risk observational cohort. The proportion and confidence interval will be estimated using generalized linear models adjusting for clustering.

- 9.5.2 **Primary outcome 2:** This aim (**PA1**) will be analyzed using contrasts from a linear mixed models analysis for 6-month back-related function (Oswestry) controlling for baseline Oswestry and the block set (see Randomization). The intervention will first be explored by time interaction, and then proceed to a main effects model with only group and time. For the secondary aims (**SA4** and **SA5**) patient-centered outcomes, such as functional status, would use general linear models if deemed appropriate based on normality assumptions. If normality is hugely violated, a cutpoint for 'response' will be applied.

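### H5 predicts benefit within the depression and low-SES subgroups but mentions only absent interactions for obesity and smoking; with no arm-by-subgroup interaction planned, a uniform effect can be read as subgroup-specific benefit

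*Combined protocol and SAP*

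**What the plan says.** SA5, in 9.1.12, "is to conduct subgroup analyses for PA1-2 and SA3 on patients with lower socioeconomic status" and on smoking, depression and obesity. H5, its hypothesis, treats the four factors in two ways.

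- **Depression and low SES.** H5 predicts an effect inside the subgroup: less transition, and superiority over GBC alone "for improving functional outcomes and reducing LBP-related medical resource utilization for the subgroup of patients with depression or low socioeconomic status" (1.2.5).
- **Obesity and smoking.** H5 says that "group x obesity or smoking interactions are not expected". The reason given is that PIPT is not aimed at these conditions and that their role in progression is unclear. The restatement in 9.1.13 leaves out smoking: "group x obesity interactions are not expected".

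On power, 3.4 promises that "Adequate enrollment will be assured to have statistical power to conduct subgroup analyses of patients with lower socioeconomic status" and the comorbidity subgroups. Section 9.2.4 is more guarded: "Detecting an interaction effect the same size as the overall intervention effect would require a four-fold increase in the effective sample size", which it calls infeasible. It then relies on effects within subgroups: "There will be sufficient power to detect stronger intervention effects in some" of the pre-specified subgroups, provided that the cohort splits evenly.

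On analysis, 9.4.1 to 9.4.3 list SA5 among the comparisons of intervention with comparator clinics. Section 9.5.1 says that the SA4 and SA5 analysis "will be largely descriptive assessing the proportion of patients who transition to chronic LBP among the low and moderate risk observational cohort". Sections 9.5.2 and 9.5.3 give SA5 general linear models and an approach similar to that for SA3. The only interaction named in 9.5 is intervention by time. There is no decision rule, alpha or multiplicity statement for H5.

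**The concern.** The contrast in H5, and the reason given for it, invite the reading that depression and low SES change the benefit of PIPT while obesity and smoking do not. That is a statement about effect modification, and only an interaction bears on it. A significant result inside one subgroup does not show that the subgroup differs from other patients. A non-significant interaction, in a trial that says it is not sized for interactions, does not show that there is no difference.

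If PIPT helps everyone equally, both halves of H5 tend to come out as predicted. A report could then describe benefit in depressed or low-SES patients as hypothesised, and no modification by obesity or smoking, without evidence that any subgroup differs from another. Decisions about whom to refer could follow from that pattern.

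**Working it through.** **Inputs.** From 9.2.2 and 9.2.3: 60 clinics, 30 per arm; 1,860 enrolled; 40% non-response; cluster-size CV 0.65; ICC 0.05; control rate 25–30%; 40% relative reduction. From Table 3: underserved 665/2464 = 27%, obesity 640/2464 = 26%, smoking 493/2464 = 20%, depression 184/2464 = 7.5%. These shares describe the low/medium-risk cohort; using them for the RCT cohort is an assumption. So is two-sided 0.05, which the plan states only for Table 3.

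**1. The plan's own figures.** Effective n per arm = 30n / (1 + (n − 1) × 0.05).
- n = 14: 420/1.65 = 254.5; 25% v 15% gives 80.7% power.
- n = 10: 300/1.45 = 206.9; 30% v 18% gives 81.8%.

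The stated power of just over 80% reproduces at these points (25% v 15% at n = 10 gives 72%). From enrolment, completers per clinic are 1860 × 0.6/60 = 18.6. The design effect is 1 + ((0.65² + 1) × 18.6 − 1) × 0.05 = 2.273. Effective n per arm is 558/2.273 = 245.5, with power 79–88%.

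The four-fold figure also reproduces. The interaction variance is v/(Nf) + v/(N(1 − f)) = (v/N)/(f(1 − f)), which is 4 times v/N at f = 0.5. It is 5.1 times at f = 0.27 and 14.5 times at f = 0.075, so four-fold is the best case.

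**2. Power inside a subgroup under a uniform 40% reduction.** Use m = 18.6f completers per clinic in the same design-effect formula.

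| Share | m | Effective n per arm | Power, control 25% to 30% |
|---|---|---|---|
| 50% | 9.3 | 173.1 | 64–75% |
| 27% (underserved) | 5.02 | 115.2 | 47–57% |
| 7.5% (depression) | 1.39 | 39.7 | 20–24% |

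**3. How often a uniform effect produces the H5 pattern.** Simulation on transition only: 60 clinics, beta-binomial outcomes, CV 0.65, ICC 0.05, 3,000 trials per setting, with a cluster-robust linear test standing in for the planned mixed model. The pattern is a significant benefit in depression or SES (or in both), with obesity and smoking interactions both non-significant.

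| Shares | Either subgroup | Both subgroups |
|---|---|---|
| Table 3 | 49–58% | 11–15% |
| Table 3, depression raised to 30% | 58–68% | 28–38% |
| Even splits | 69–75% | 48–56% |

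In each cell the lower value is 25% v 15% and the upper is 30% v 18%. No subgroup differs from another in any of these settings.

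**4. No effect at all.** Two subgroups × three outcomes = 6 tests. If independent, the chance of at least one result favouring PIPT is 1 − 0.975⁶ = 14.1%. With outcome correlation up to 0.7 and subgroup correlation up to 0.3 it falls to 10%. The full pattern on transition alone occurs in about 5–6% of trials.

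**5. Power of the interaction test**, for an interaction as large as the overall effect. The lower range applies the full design effect (N = 245.5 per arm). The higher range lets the clinic effect cancel within clinic (N = 558/0.95 = 587 per arm).

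| Share | Full design effect | Clinic effect cancels |
|---|---|---|
| 50% | 29–35% | 58–68% |
| 27% (underserved) | 24–29% | 48–58% |
| 7.5% (depression) | 11–13% | 21–25% |

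**The case against.** The strongest reply is that H5, read literally, claims benefit in these subgroups and not greater benefit there than elsewhere. Under a uniform effect that claim is true, and so is the absence of an obesity or smoking interaction. The rates in step 3 are then partly power to detect something true. This stands: the harm lies in the differential reading, which is an inference from the contrast H5 draws. The inference is a natural one, because H5 justifies the contrast by what PIPT targets, and the analysis section offers nothing to separate the two readings.

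A second reply is that 9.2.4 already concedes the point: interactions cannot be powered, and expectations are limited to stronger effects in some subgroups. That is fair, but the concession covers all four factors. It argues for estimates with intervals, not for relying on tests within subgroups. The even split on which 9.2.4 depends is also not what Table 3 shows for any factor.

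Third, switching to interactions does not by itself control multiplicity, since several interaction tests also give false positives. This stands, and is why the exploratory description belongs in the fix.

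A reader might also infer that H5 is a confirmatory claim tested at full alpha. The documents do not say so. H5 sits under secondary objectives, no alpha is assigned to it, and 9.5.1 names SA5 when it calls the analysis largely descriptive, although that sentence goes on to describe only the low/moderate-risk cohort. Nor do they plan a test by which obesity and smoking would be judged; they state only an expectation.

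**Conclusion.** The point holds as a gap in specification with a cheap remedy. H5 sets different standards for two pairs of factors, and no arm-by-factor interaction is planned for any of them. A uniform 40% reduction can therefore readily satisfy H5: in 49–58% of trials on transition if one subgroup suffices, and 11–15% if both are needed, at the Table 3 shares. H5 does not say which applies. Section 2.3.3 describes high-risk patients as having comorbid depression, so 7.5% may be too low for the RCT cohort; a larger share raises these rates.

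Two stronger readings should be resisted. One is that chance alone will usually reproduce the predicted pattern. It does so in about 5–6% of trials on transition, and the 10–14% for any favourable result among six tests rests on an assumed alpha. The other is that a subgroup finding could stand in for a null primary result. Nothing in the documents allows a subgroup result to replace H1 or H2, and 9.2.5 commits treatment comparisons to intention-to-treat analysis and CONSORT cluster reporting.

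**What to change.** In 1.2.5, 9.1.13 and 9.5.1 to 9.5.3:

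- Assess SES, depression, obesity and smoking the same way, by the arm-by-factor interaction in each outcome's mixed model. Restore smoking in 9.1.13.
- Report each interaction estimate and the effects in both levels of the factor, with 95% CIs, side by side.
- Describe SA5 and H5 as exploratory.
- Base any statement that the effect differs by subgroup on the interaction. Subgroup estimates may still be reported as such.
- State that a non-significant interaction is not evidence of no modification.

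The cost is four interaction terms per outcome and some wording, with no new data. The downside is low interaction power: about 11–25% for depression at 7.5% and 24–58% for underserved patients at 27%, for an interaction as large as the overall effect. H5 will mostly yield estimates with wide intervals, and the plan should say so.
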